4. ANALYSIS SETS

CCI

[figure not shown]

CONFIDENTIAL

212458 (MENACWY=CCI -001 PRI)

Statistical Analysis Plan Amendment 5

CCI

[figure not shown]

CONFIDENTIAL

212458 (MENACWY=CCI -001 PRI)

Statistical Analysis Plan Amendment 5

CCI

[figure not shown]

CONFIDENTIAL

212458 (MENACWY=CCI -001 PRI)

Statistical Analysis Plan Amendment 5

CCI

[figure not shown]

CONFIDENTIAL

212458 (MENACWY=CCI -001 PRI)

Statistical Analysis Plan Amendment 5

CCI

CCI

5. STATISTICAL ANALYSES

Standard data derivation rules and stat methods are described in section 10.1 while the study specific data derivation rules and stat methods are described in section 9.

5.1. Disposition of subjects

5.1.1. Analysis of disposition of subjects

Number of subjects enrolled, vaccinated subjects (at least 1 vaccination, full vaccination course), reason for early withdrawal, FAS, and PPS will be described by vaccine group.

5.2. Analysis of demography and baseline characteristics

5.2.1. Analysis planned in the protocol

Demography and baseline characteristics analysis are not described in the protocol.

5.2.2. Additional considerations

Descriptive statistics (mean, standard deviation, median, minimum and maximum) for age, height, weight, and body mass index (BMI) at enrolment will be calculated overall and by vaccine group.

Distributions of subjects by sex, race, ethnic origin will be summarised overall and by vaccine group.

5.3. Primary endpoints

[figure not shown]
CCI

CONFIDENTIAL

212458 (MENACWY=CCI -001 PRI)

Statistical Analysis Plan Amendment 5

CCI

[figure not shown]

CONFIDENTIAL

212458 (MENACWY=CCI -001 PRI)

Statistical Analysis Plan Amendment 5

CCI

CONFIDENTIAL

212458 (MENACWY=CCI -001 PRI)

CCI

CCI

[figure not shown]

CONFIDENTIAL

212458 (MENACWY=CCI -001 PRI)

Statistical Analysis Plan Amendment 5

CCI

CCI

5.3.2. Additional considerations

NA

CCI

5.4. Secondary endpoints

5.4.1. Analysis planned in the protocol

[figure not shown]
5.4.1.1. Phase I (Safety Lead-in)

NA

[figure not shown]
CONFIDENTIAL

212458 (MENACWY=CCI -001 PRI)

CCI

CCI

[figure not shown]
5.4.1.3. Phase II (Sourcing)

NA

CONFIDENTIAL

212458 (MENACWY=CCI -001 PRI)

CCI

[figure not shown]

CONFIDENTIAL

212458 (MENACWY=CCI -001 PRI)

Statistical Analysis Plan Amendment 5

CCI

[figure not shown]

CONFIDENTIAL

212458 (MENACWY=CCI -001 PRI)

Statistical Analysis Plan Amendment 5

CCI

[figure not shown]

CONFIDENTIAL

[figure not shown]
212458 (MENACWY=CCI -001 PRI)

Statistical Analysis Plan Amendment 5

[figure not shown]
CCI

CCI

CCI

9.1. Data derivation

NA

9.2. Statistical method

NA

9.2.1. Adjusted GMT ratios

[figure not shown]
NA

9.2.2. Vaccine efficacy

[figure not shown]
NA

10. ANNEXES

CCI

CCI

**10.1.2.2. Laboratory data**

Missing laboratory results (including immunological data) will not be replaced.

10.1.2.3. Daily recording of solicited events**10.1.2.3.1. Studies with electronic diaries**

For studies using electronic diaries for the collection of solicited events, a solicited event will be considered present only when a daily recording of grade 1 or more is present.

10.1.2.4. Unsolicited adverse events

Unsolicited adverse event summaries are including serious adverse events unless specified otherwise.

Missing severity, relationship with study vaccine, and outcome of unsolicited adverse events will not be replaced and will appear as 'UNKNOWN' when displayed in a statistical output.

10.1.3. Data derivation**10.1.3.1. Age at first dose in days**

When age at first dose is to be displayed in days, it will be calculated as:

Age = date of first dose minus date of birth

10.1.3.2. Age at first dose in months

When age at first dose is to be displayed in months, it will be calculated as the number of complete calendar months between the date of birth (DOB) and the date of first dose. For example:

DOB = 10JUN2017, Date of first dose = 09JUL2018 -> Age = 12 months

DOB = 10JUN2017, Date of first dose = 10JUL2018 -> Age = 13 months

10.1.3.3. Age at first dose in years

When age at first dose is to be displayed in years, it will be calculated as the number of complete calendar years between the date of birth and the date of first dose. For example:

DOB = 10SEP1983, Date of first dose = 09SEP2018 -> Age = 34 years

DOB = 10SEP1983, Date of first dose = 10SEP2018 -> Age = 35 years

10.1.3.4. Weight

Weight will be presented in kilograms. Weights reported in pounds will be converted as follows:

Weight in kilograms = Weight in pounds / 2.2

10.1.3.5. Height

Height will be presented in centimetres. Heights reported in feet and inches will be converted as follows:

Height in centimetres = Height in inches x 2.54

10.1.3.6. Body mass index (BMI)

BMI will be calculated as follows:

BMI = (Weight in kilograms) / (Height in meters)²

10.1.3.7. Temperature

Temperatures will be presented in degrees Celsius (°C). Temperatures reported in degrees Fahrenheit (°F) will be converted as follows:

Temperature (Celsius) = ((Temperature (Fahrenheit) - 32) x 5)/9

10.1.3.8. Numerical serology results

Numerical serology results will be derived from the content of IS.ISORRES in the SDTM dataset. For assays with a specific cut-off, the following derivation rules apply:

IS.ISORRES	Derived value
“NEG”, “-”, or “(-)”	cut-off/2
“POS”, “+”, or “(+)”	cut-off
“< value” and value is \leq assay cut-off	cut-off/2
“< value” and value is $>$ assay cut-off	value
“> value” and value is $<$ assay cut-off	cut-off/2
“> value” and value is \geq assay cut-off	value
“value” and value is $<$ cut-off	cut-off/2
“value” and value is \geq cut-off	value
All other cases	missing

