Abbreviations: AE, Adverse event; SAE, Serious adverse event; AESI, Adverse event of special interest; ELISA, enzyme-linked immunosorbent assay; GMC, geometric mean concentrations; enc-hSBA, endogenous complement human serum bactericidal assay; GMT, geometric mean titre; GMR, geometric mean ratio; hSBA, human serum bactericidal assay; LOD, limit of detection; LLOQ, lower limit of quantitation.

Note 1: MenB immune response will be assessed against *N. meningitidis* serogroup B indicator strains CCI

Note 2: Evaluation of the tertiary objectives may or not be performed. If the tertiary objectives are evaluated, it may be assessed in a subset of participants using remaining serum after the primary and secondary analyses have been completed; no additional blood samples will be collected from participants.

*All statistical criterion linked to evaluation of the objectives can be found in Section 9.4.

**For the serogroup A C, W, Y and serogroup B evaluations, the 4-fold rise (for serogroup B - per each indicator strain) is defined as:

- a post-vaccination hSBA titre ≥ 16 for participants with a pre-vaccination hSBA titre < 4 ,
- a post-vaccination hSBA titre ≥ 4 times the LLOQ for participants with a pre-vaccination hSBA titre $\geq \text{LOD}$ but $< \text{LLOQ}$, and
- a post-vaccination hSBA titre ≥ 4 times the pre-vaccination hSBA titre for participants with a pre-vaccination hSBA titre $\geq \text{LLOQ}$

[†]The primary objective of immunological NI of the [REDACTED] vaccine to MenACWY will be evaluated only in participants without a previous MenACWY vaccination (unprimed). All other primary and secondary objectives will be evaluated in participants with and without previous MenACWY vaccination (primed/unprimed).

CCII

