10.1.3.9. Geometric mean titres (GMTs) and concentrations (GMCs)

Geometric Mean Titre (GMT) or Concentration (GMC) calculations are performed by taking the inverse logarithm of the mean of the log titre or concentration transformations. Antibody titres or concentrations below the cut-off of the assay will be given an arbitrary value of half the cut-off of the assay for the purpose of GMT/GMC calculation. Cut-off values are defined by the laboratory before the analysis.

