10.1.3.10. Calculation of the 4-fold rise

The 4-fold rise for serogroups A, C, W, Y and for serogroup B indicator strains is defined as:

- a post-vaccination hSBA titre \geq 4 times the LOD or \geq LLOQ, whichever is greater, for subjects with a pre-vaccination hSBA titre $<$ LOD,
- a post-vaccination hSBA titre \geq 4 times the LLOQ for subjects with a pre-vaccination hSBA titre \geq LOD but $<$ LLOQ, and
- a post-vaccination hSBA titre \geq 4 times the pre-vaccination titre for subjects with a pre-vaccination hSBA titre \geq LLOQ.

The LOD and the LLOQ depend on the serogroup and the indicator strain, and are still under evaluation while this document is being amended.

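### SAP 10.1.3.8 converts a result reported as '<X' (X above the assay cut-off) into X, so a sample reported below the LLOQ could be counted as reaching it unless status is read from the reported result

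*SAP*

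**What the plan says.** SAP 10.1.3.8 is a general rule for turning reported serology results into numbers. Its lead-in is "For assays with a specific cut-off, the following derivation rules apply". Three rows matter here:

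- Row 3: '<X' with X at or below the cut-off becomes half the cut-off.
- Row 4: '<X' with X above the cut-off becomes X.
- Row 8: a plain number at or above the cut-off is kept.

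SAP 10.1.3.9 says that titres below the cut-off "will be given an arbitrary value of half the cut-off of the assay for the purpose of GMT/GMC calculation". It adds: "Cut-off values are defined by the laboratory before the analysis". SAP 10.1.3.10 defines the 4-fold rise with three pre-vaccination classes: below LOD, from LOD to below LLOQ, and LLOQ or above. It says that the LOD and LLOQ "are still under evaluation while this document is being amended".

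SAP section 5 states that "the study specific data derivation rules and stat methods are described in section 9". The entry under "9.1. Data derivation" is NA. SAP section 2 lists the percentage with hSBA titre at or above the LLOQ as a secondary endpoint for serogroups A, C, W and Y and for the serogroup B indicator strains. Protocol 9.2.2 brings secondary results into the choice of formulation and schedule once the primary objectives have succeeded.

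**The concern.** A report of '<X' means that the titre did not reach X. Row 4 gives it the value X, and the endpoint's threshold is inclusive. A sample reported '<LLOQ' would then pass a test that its own report says it failed.

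No visible text blocks this. The half-cut-off rule in 10.1.3.9 covers only results below the cut-off and is written for GMT/GMC. Section 9.1 adds nothing. The cut-off, LOD and LLOQ are used as separate terms, and no visible sentence equates the cut-off with the LLOQ.

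At stake is the accuracy of the percentage at or above the LLOQ, which feeds the selection of formulation and schedule.

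**Working it through.** **Inputs.** The conversion rows come from SAP 10.1.3.8, the classes from 10.1.3.10, the endpoint from SAP section 2, and the arm size of 196 from Protocol Table 13. No numeric cut-off, LOD or LLOQ is visible in the SAP. For illustration I assume LOD 4, because the protocol's first 4-fold-rise class is a titre below 4 (Table 11 footnote, "for participants with a pre-vaccination hSBA titre"), and LLOQ 8 unless stated otherwise.

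**Step 1: one '<LLOQ' result.** With cut-off 4, row 4 applies: '<8' becomes 8, and 8 ≥ 8 counts as reaching the LLOQ. With cut-off 8, row 3 applies: '<8' becomes 4, correctly below.

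**Step 2: when the error can occur.**

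| Cut-off | In-between results reported as | Status taken from | Result for % ≥ LLOQ |
|---|---|---|---|
| = LLOQ | '<LLOQ' | converted value | correct |
| < LLOQ | numbers | converted value | correct (row 8) |
| < LLOQ | '<LLOQ' | converted value | counted as ≥ LLOQ |
| any | '<LLOQ' or numbers | reported result | correct |

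A result '<X' with X above the LLOQ falls under row 4 whether the cut-off is the LOD or the LLOQ. It is then counted as ≥ LLOQ, and this is wrong for those samples whose true titre is below the LLOQ.

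**Step 3: size within one arm.** Counted % = true % + share of samples reported '<LLOQ'. Shares of 1, 5 and 10% add 1, 5 and 10 points: 0.01 × 196 ≈ 2, 0.05 × 196 ≈ 10 and 0.10 × 196 ≈ 20 participants. For '<X' with X above the LLOQ, the addition is at most the share.

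**Step 4: differences between arms.** Assume log2-normal titres with m = log2(GMT). Then true % ≥ 8 is 1 − Φ((3 − m)/SD), and the share from 4 to below 8 is Φ((3 − m)/SD) − Φ((2 − m)/SD). If every in-between result is reported '<8':

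| GMT / SD(log2) | True % ≥ 8 | In between | Counted % |
|---|---|---|---|
| 2 / 1.5 | 9.1 | 16.1 | 25.2 |
| 4 / 1.5 | 25.2 | 24.8 | 50.0 |
| 8 / 2 | 50.0 | 19.1 | 69.1 |
| 32 / 2 | 84.1 | 9.2 | 93.3 |

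The difference between two arms changes by the difference in their in-between shares:

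- GMT 8 vs 32: 34.1 + (9.2 − 19.1) = 24.2 points, narrower.
- GMT 2 vs 4: 16.1 + (24.8 − 16.1) = 24.8 points, wider.
- GMT 2 vs 8: 40.9 + (19.1 − 16.1) = 43.9 points, wider.

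**Step 5: primary 4-fold rise.** Take '<LLOQ' to mean between LOD and LLOQ. For a pre-vaccination titre below LOD the bar is max(4 × LOD, LLOQ).

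- LLOQ 8: the bar is 16. A post-dose '<8' becomes 8 and fails, as it should.
- LLOQ 16: the bar is 16. A post-dose '<16' becomes 16 and passes wrongly.
- Other pre-vaccination classes need at least 4 × LLOQ, so a post-dose value of LLOQ fails.
- A pre-dose '<LLOQ' needs 4 × LLOQ whether it stays in the middle class or is moved to LLOQ.

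So '<LLOQ' reports change this endpoint only if LLOQ ≥ 4 × LOD.

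**Step 6: results that cannot be placed.** Suppose 5 of 100 samples are '<X' with X above the threshold, 80 of the 100 truly meet it, and a fraction q of the 5 do. Row 4 gives 80 + 5(1 − q), that is 80 to 85%. Counting them as not meeting gives 80 − 5q, that is 75 to 80%. Treating them as missing gives (80 − 5q)/95, that is 78.9 to 84.2%.

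**The case against.** The '<LLOQ' miscount needs three things that the documents do not confirm: status taken from converted values, a cut-off below the LLOQ, and in-between samples reported as the string '<LLOQ'. The laboratory assay table, the assay descriptions, the secondary-endpoint methods and the opening of SAP 10.1 are partly or wholly redacted and may answer all three. Text hidden by redaction is not absent from the plan. This stands.

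The middle class of 10.1.3.10, which asks for 4 "times the LLOQ for subjects with a pre-vaccination hSBA titre" from LOD to below LLOQ, also points away from the worst case. If every in-between result were reported '<LLOQ' and moved to the LLOQ, that class would be empty. This stands too, but it does not clear the rule. With the cut-off at the LLOQ, every result below it becomes the single value LLOQ/2, and converted values could not separate the first two classes. The class structure therefore fits in-between titres reported as numbers, or classification from the reported result. Neither is visibly stated.

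It can also be said that 10.1 holds generic rules and that a sample reported '<LLOQ' plainly fails the endpoint's definition. That is the sensible intention, but the text should say it, because row 4 read literally gives the opposite.

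A reader might infer that the error makes arms look more alike. Step 4 shows that the difference can shrink or widen. A reader might also infer that the primary non-inferiority result is at risk. The first class of 10.1.3.10 does allow for an LLOQ above 4 × LOD, but nothing shows that any serogroup has one.

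**Conclusion.** The point holds as a conditional one. Row 4 is a stated general rule that, applied literally to the inclusive LLOQ endpoints, can score a result reported below X as reaching X, and no visible text overrides it. It is not a demonstrated miscount. The conditions are open and the frequency may be zero.

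If they hold, the percentage at or above the LLOQ is too high by exactly the share of '<LLOQ' results so treated, and by at most the share of '<X' results with X above the LLOQ. The direction of any effect on arm comparisons cannot be predicted. The distributions and limits used in Steps 4 and 5 are assumptions, not estimates for this trial. The endpoint is secondary, so the consequence is for the selection of formulation and schedule. The correction is nearly free and worth making; confidence is medium because of the redactions.

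**What to change.** Add to SAP 10.1.3.8:

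1. Status at or above the LLOQ and 4-fold-rise response are assigned from the reported result, before any numeric substitution.
2. A result reported '<X' is never counted as meeting a threshold at or above X, so '<LLOQ' is always below the LLOQ.
3. Where X is above the threshold and the result cannot be placed, it is not automatically counted as meeting the threshold. The number of such results is reported by group and visit, with a sensitivity analysis treating them as not meeting and as missing.

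Leave the GMT/GMC substitution unchanged. If the redacted text already states how the cut-off relates to the LOD and LLOQ, a cross-reference is enough for that part.

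The cost is a few lines of SAP text, one status flag, one count table and one sensitivity table. The downside is small: some unplaceable results that truly meet the threshold may be counted as not meeting it, by up to 5 points in the 5% example of Step 6. Row 4 can err by as much in the other direction. For '<LLOQ' against the LLOQ threshold the rule is exact, and if no such strings occur it changes nothing.

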10.1.3.9. Geometric mean titres (GMTs) and concentrations (GMCs)

Geometric Mean Titre (GMT) or Concentration (GMC) calculations are performed by taking the inverse logarithm of the mean of the log titre or concentration transformations. Antibody titres or concentrations below the cut-off of the assay will be given an arbitrary value of half the cut-off of the assay for the purpose of GMT/GMC calculation. Cut-off values are defined by the laboratory before the analysis.

10.1.3.10. Calculation of the 4-fold rise

The 4-fold rise for serogroups A, C, W, Y and for serogroup B indicator strains is defined as:

- a post-vaccination hSBA titre \geq 4 times the LOD or \geq LLOQ, whichever is greater, for subjects with a pre-vaccination hSBA titre $<$ LOD,
- a post-vaccination hSBA titre \geq 4 times the LLOQ for subjects with a pre-vaccination hSBA titre \geq LOD but $<$ LLOQ, and
- a post-vaccination hSBA titre \geq 4 times the pre-vaccination titre for subjects with a pre-vaccination hSBA titre \geq LLOQ.

The LOD and the LLOQ depend on the serogroup and the indicator strain, and are still under evaluation while this document is being amended.

10.1.3.11. Onset day

The onset day for an event (e.g., AE, concomitant medication/vaccination) is the number of days between the last study dose and the start date of the event. This is 1 for an event occurring on the same day as a study dose (and reported as starting after study dose).

10.1.3.12. Duration of events

The duration of an event with a start and end date will be the difference between the start and end date plus one day, i.e., an event that starts on 03MAR2018 and ends on 12MAR2018 has a duration of 10 days.

10.1.3.13. Counting rules for combining solicited and unsolicited adverse events

Unsolicited adverse events with missing administration site flag will be considered systemic.

Multiple events with the same preferred term which start on the same day are counted as only one occurrence.

10.1.3.14. Counting rules for occurrences of solicited events

When the occurrences of solicited events are summarized, each event recorded as having occurred during a specific period will be counted as only one occurrence regardless of the number of days on which it occurs. In case of multiple reporting for the same solicited adverse event, the worst reported grade will be considered.

At visit 1 of Control group in Phase II F&SF two vaccines are injected, one in either arm. Therefore, administration site adverse events imputed during the first seven days after visit 1 must be related to a specific arm and vaccine. For subjects where, instead, it is not possible to uniquely associate one or more records of administration site adverse events to one of the two vaccines, then all the administration site events recorded by those subjects during the first seven days after vaccination will be excluded from the analysis. In this way, ambiguous records will not contribute to the denominator – nor to the numerator – when calculating frequencies and percentages of administration site adverse events at visit 1 of Control group. Systemic adverse events will still be reported as usual, as their records are never associated to a specific arm.

10.1.4. Display of decimals**10.1.4.1. Percentages**

Percentages and their corresponding confidence limits will be displayed with:

- no decimals when there are fewer than 50 subjects in each tabulated group
- one decimal when there are at least 50 subjects in at least one tabulated group
 - Exceptions will be made for percentages that are not 0% or 100% but appear as 0% or 100% due to rounding. For these specific cases the number of decimals will be increased until the displayed value is no longer 0% or 100%. Examples are given in the following table.

n/N	Displayed percentage
10/45	22%
1/45	2%
10/55	18.2%
1/55	1.8%
1/300	0.3%
1/3000	0.03%
1/30000	0.003%
299/300	99.7%
2999/3000	99.97%
29999/30000	99.997%

- The display of additional decimals for values close to 0% or 100% will be applied only to point estimates and not confidence limits, which can be rounded and displayed as 0% or 100%.
- Values of exactly 0% or 100% will be presented with no decimals regardless of the number of subjects per tabulated group.

10.1.4.2. Differences in percentages

Differences in percentages and their corresponding confidence limits will be displayed with one more decimal than the maximum number used to display the individual percentages, for example the difference between two percentages displayed with one decimal will be displayed with two decimals.

10.1.4.3. Demographic/baseline characteristics statistics

The mean, median, and standard deviation for continuous baseline characteristics (height, weight, body mass index (BMI), pre-dose body temperature) will be presented with one decimal.

The minimum and maximum values and quartile values (if required) will be presented with the same number of decimals as the observed values.

The maxima and minima of transformed height/weight variables will be displayed without decimals, with the exception of infant studies where one decimal will be displayed for the transformed weight.

The maximum and minimum of transformed body temperatures will be displayed with one decimal.

10.1.4.4. Serological summary statistics

The number of decimals used when displaying geometric mean titres (GMT) or concentrations (GMC) and their confidence limits is shown in the following table:

GMT or GMC value	Number of decimals to display
<0.1	3
≥0.1 and <10	2
≥10 and <1000	1
≥1000	0

When multiple categories of GMT or GMC values are present in the same table, the number of decimals displayed should match that of the smallest category (i.e., the one with the higher number of decimals). For example, if GMT or GMC values of <0.1 appear in the same table as values of ≥0.1 and <10, 3 decimals should be displayed for both.

GMT or GMC group ratios and their confidence limits will be displayed with 2 decimals regardless of the actual values.

CCI

